# Phase 2 Sample Size

A total of 140 subjects will be randomized in a 1:1 ratio to receive either CMP-001 in combination with nivolumab (Arm A) or nivolumab monotherapy (Arm B). A sample size of 140 subjects provides 80% power to detect an absolute treatment difference of 25% with a 2-sided alpha level of 0.05, assuming that the ORR in Arm A is 65% and the ORR in Arm B is 40%. The sample size calculation is performed in PASS-2020 for testing 2 independent proportions using the continuity corrected Z-test with pooled variance.

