Note: 100DFU = 100-Day Follow-up; EOT = End of Treatment; LTSFU = Long-Term Survival Follow-up; IT = intratumoral; IV = intravenous; PTFU = Post-treatment Follow-up; Q3W = every 3 weeks; Q6W = every 6 weeks; Q12W = every 12 weeks; QW = weekly; W1D1 = Week 1 Day 1; W10D1 = Week 10 Day 1.

- a. The first CMP-001 dose (W1D1) may be administered subcutaneously or by IT injection at the discretion of the Investigator.
- b. Disease assessments performed predose beginning at W10D1 (-7 days) and repeated Q6W on treatment and then Q12W for subjects on treatment more than 1 year.

B. Study Population

See Protocol Sections 4.1 and 4.2 for a complete list of the inclusion/exclusion criteria.

C. Sample Size Status

Given the early termination of site activation and study enrollment since 24Jun2022 per Sponsor's decision, the trial has been changed to a Phase 2 study with all the analyses being exploratory. Subjects who have provided written informed consent may complete Screening and be randomized if they meet all eligibility criteria at the discretion of the Sponsor or their representatives. With the enrollment of the last subject on 01Jun2022, the subject status of this study is as follows:

• Screened: 27 subjects

Screen failure: 7 subjectsRandomized: 20 subjects

• Treated: 20 subjects

A total of 20 subjects were randomized in a 1:1 ratio to receive either CMP-001 in combination with nivolumab (Arm A) or nivolumab monotherapy (Arm B) with 9 subjects in Arm A and 11 subjects in Arm B as of the early termination of the study enrollment.

D. Treatment Randomization

Subjects who complete Screening procedures and meet inclusion/exclusion criteria will be randomized in a 1:1 ratio to Arm A (CMP-001 in combination with nivolumab) or Arm B (nivolumab monotherapy) using an Interactive Web Response System (IWRS) and stratified by the following factors:

- TNM Stage AJCC Cancer Staging Manual Eighth Edition (M0/M1a/M1b versus M1c/M1d)
- Tumor PD-L1 expression (Tumor Proportion Score, TPS %: ≥ 5% versus < 5%)

Regeneron Pharmaceuticals Inc. / Protocol: CMP-001-011 IQVIA Biotech (Confidential) Project # SZA58924

During the Screening process, subject-specific values will be recorded for each of the 2 stratification variables. Based on the entered values, the subject will be assigned to a treatment group according to a preprogrammed randomization schedule, which is designed to balance the 2 treatment groups by each variable to the extent possible.

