DOR is only defined for subjects who have a confirmed BOR of CR or PR. Subjects with an overall response of CR or PR must have a repeated tumor assessment performed no less than 4 weeks after the criteria for response are first met. The first date on which a CR or PR response is noted will be used to calculate DOR, rather than the date of the confirmatory tumor assessment. Subjects who do not have PD or death will be censored at the date of their last disease assessment. Details of the censoring rules are provided in Table 1.

DOR will be calculated as follows:

DOR (months) = (Event/Censoring Date – Response Start Date + 1) / 30.4375

The number and percentage of subjects will be further tabulated according to the response duration of the subject (follow-up time on disease assessment post the initial response of a subject):

- < 6 months
- 6 to < 9 months
- 9 to < 12 months
- 12 to < 18 months
- \geq 18 months

Regeneron Pharmaceuticals Inc. / Protocol: CMP-001-011 IQVIA Biotech (Confidential) Project # SZA58924

DOR will be analyzed using the Kaplan-Meier method by treatment arm for the ITT Analysis Set. The median DOR per Kaplan-Meier estimate with two-sided 95% CI calculated using Brookmeyer and Crowley method will be provided. The event-free rate with two-sided 95% CI using Greenwood's formula will be calculated for selected timepoints (i.e., 6 and 12 months). The reasons for censoring will be summarized categorically. A Kaplan-Meier plot of DOR will be generated by treatment arm. Besides, the analysis of DOR based on RECIST v1.1 as determined by Investigator assessment will also be performed.

Progression-Free Survival (PFS). Progression-free survival is defined as the time from date of randomization to the date of documented PD based on RECIST v1.1 as determined by BICR or death from any cause, whichever occurs first. Subjects who are alive and progression-free at the time of analyses will be censored in the analyses. Overall response assessment evaluated after subsequent new anti-cancer therapy will not be considered for PFS calculation.

PFS will be calculated as follows:

PFS (months) = (Event or Censoring Date – Date of Randomization + 1) / 30.4375

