All events of RECIST v1.1 disease progression or death will be counted regardless of whether the event occurs while the subject is on study treatment or previously discontinued the study treatment. Subjects who do not experience disease progression or death as of the analysis cutoff date or final database lock will be censored at the date of the last adequate tumor assessment. Date of censoring for these subjects will be based on the last tumor assessment prior to missing the assessments. Censoring rules are summarized in Table 1. If a subject meets the criteria for more than one censoring rule, PFS will be censored at the earliest censoring date. Unless specified otherwise, the analysis methods described for DOR will be used for PFS. Additionally, the analysis of PFS based on RECIST v1.1 as determined by Investigator assessment will also be performed.

Overall Survival (OS). Overall survival will be calculated as the time from the date of randomization to the date of death due to any cause. Subjects who are alive or lost to follow-up as of the analysis cutoff date will be censored at the time of the last study contact date (i.e., date of last known alive). The last contact date will be derived as detailed in Table 2.

Based on these considerations, OS will be calculated as follows: OS (months) = (Death or Censoring Date – Date of Randomization + 1) / 30.4375

Regeneron Pharmaceuticals Inc. / Protocol: CMP-001-011 IQVIA Biotech (Confidential) Project # SZA58924

OS will be analyzed using the Kaplan-Meier method by treatment arm of the ITT Analysis Set. A Kaplan-Meier plot of OS will be generated for each treatment arm. The analysis methods described for DOR will be used for OS, unless specified otherwise.

Disease Control Rate (DCR). The confirmed disease control rate is defined as the proportion of subjects in each treatment arm in the analysis set who have a confirmed best response of CR, PR, or stable disease (SD) lasting at least 4 months. Per RECIST v1.1, CR or PR must be confirmed by a confirmatory assessment performed at least 4 weeks after the initial response. In the case of SD, measurements must have met the SD criteria at least once after study entry at a minimum interval of 6 weeks. Overall response assessment evaluated after subsequent new anti-cancer therapy will not be considered for DCR calculation.

DCR will be analyzed in a similar manner as ORR. Specifically, DCR and the associated 95% Clopper-Pearson CIs will be summarized.

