DCR: DCR will be analyzed in a similar manner as ORR. Specifically, DCR and the associated 95% Clopper-Pearson CIs will be summarized.

DOR, PFS, OS, iDOR and iPFS: The secondary endpoints for the exploratory Phase 2 study will be analyzed using the Kaplan-Meier method by treatment arm in the ITT Analysis Set. Median time-to-event with 95% CIs, and event-free rates at 6 and 12 months with 95% CIs will be estimated using Kaplan-Meier methodology. The reasons for censoring will be summarized categorically with the number and percentage of subjects tabulated. Kaplan-Meier plot will also be depicted for visualization.

The following efficacy figures will be generated to display the assessment per RECIST v1.1 by confirmed BICR for each treatment arm of the ITT Analysis set. Additional figures for the Investigator assessment may be produced.

- Swimmer's plot delineating the occurrence of the clinical outcomes of interest over time
 - Duration of treatment
 - Treatment ongoing
 - Time to BOR based on RECIST v1.1 as assessed by BICR, except that PD will be the first occurrence of PD
 - Each BOR category will be displayed in different colors
 - Time to death

Regeneron Pharmaceuticals Inc. / Protocol: CMP-001-011 IQVIA Biotech (Confidential) Project # SZA58924

- Waterfall plot depicting the best percent change in tumor burden of target lesions from baseline and BOR per RECIST v1.1 by BICR for each subject graphically
 - Tumor burden as reflected by the sum of the diameters (SOD) of all target lesions, concerning the longest diameters for extranodal lesions and short axis for lymph nodes, will be assessed at baseline and at each disease assessment after the first dose of CMP-001
 - Tumor burden change will be calculated as the percentage change in SOD of target lesions from baseline for each efficacy evaluable subject at each disease assessment
 - o Each BOR category will be displayed in different colors
- Spider plot presenting the percentage change in tumor burden from baseline for each individual subject over time
 - o Each BOR category will be displayed in different colors
- Kaplan-Meier plot displaying time-to-event on DOR, and PFS per RECIST v1.1 by BICR and OS
 - Estimate of median and the corresponding two-sided 95% CIs for median
 - o Event-free rates at selected timepoints (i.e., 6 and 12 months)
- Forest plot suggesting ORR and the associated two-sided 95% CIs

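### Greenwood 95% intervals for 6- and 12-month event-free rates break down in arms of 9 and 11 when few or no events have occurred; use an interval that stays valid at 0% and 100%

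*SAP*

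**What the plan says.** SAP Section VIII.A, Duration of Response, sets the interval: "The event-free rate with two-sided 95% CI using Greenwood's formula will be calculated for selected timepoints", with 6 and 12 months as the time points. The denominator is small by definition: "DOR is only defined for subjects who have a confirmed BOR of CR or PR".

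The PFS paragraph of the same section adds: "Unless specified otherwise, the analysis methods described for DOR will be used for PFS". The OS paragraph adds: "The analysis methods described for DOR will be used for OS, unless specified otherwise". Section VIII.C then covers DOR, PFS, OS, iDOR and iPFS together: "Median time-to-event with 95% CIs, and event-free rates at 6 and 12 months with 95% CIs will be estimated using Kaplan-Meier methodology". Greenwood is not named again there, so its use for iDOR and iPFS is an inference from VIII.C, not an explicit instruction.

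Section II.C gives the sample: "with 9 subjects in Arm A and 11 subjects in Arm B".

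The SAP does not state whether the limits are linear, log or log-log. It gives no rule for a Kaplan-Meier estimate of 0% or 100%, and no minimum number at risk. For ORR, DCR and iORR in the same arms it uses exact Clopper-Pearson limits.

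**The concern.** Greenwood's formula estimates a variance from the events seen. With no events it returns zero, however few subjects were followed. Nine of nine alive at 6 months would be reported as 100% with limits of 100% and 100%, or with no limits at all. A clear run of 9, 11 or 4 subjects is a likely result here for early OS and for DOR.

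What is at stake is the honesty of the error bars. There is no powered test and no multiplicity control, so the intervals carry the formal statement of uncertainty for these rates. The same report could show nine of nine as 66%-100% where an exact method is used and as 100%-100% where Greenwood is used.

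**Working it through.** The documents state no width or coverage for these intervals, so there is no plan figure to reproduce.

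**Inputs**
- Arm sizes 9 and 11 (SAP II.C).
- Responders: the protocol's planning ORRs of 65% and 40% (Section 9.1) give 9 × 0.65 = 5.9 and 11 × 0.40 = 4.4. Calculations use 6 and 4.
- Plausible true rates, assuming exponential curves, from the protocol's background figures:
  - OS: 5-year survival up to 45% (Section 1.1) gives 0.45^(6/60) = 0.92 and 0.45^(12/60) = 0.85.
  - DOR: median 19.9 months in a PD-1-refractory population (Section 1.2.1) gives 0.5^(6/19.9) = 0.81 and 0.5^(12/19.9) = 0.66.
  - PFS: medians of 4.1 to 6.9 months (Section 1.1) give 0.36 to 0.55 at 6 months and 0.13 to 0.30 at 12 months.

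**Formulas** (no censoring before the time point)
- Estimate S = x/n, with x subjects event-free. Greenwood's SE reduces to √[S(1−S)/n].
- Linear limits: S ± 1.96·SE.
- Log-log limits: S raised to exp(±1.96·SE/(S·|ln S|)).
- Clopper-Pearson lower limit when x = n: 0.025^(1/n).

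**Single results**
- 9/9: SE = √[1 × 0/9] = 0. Linear limits are 100%-100%. Log-log divides by ln 1 = 0 and is undefined. The exact limits are 0.025^(1/9) = 66% to 100%.
- 11/11 and 4/4 fail in the same way. Exact limits are 72%-100% and 40%-100%.
- 8/9: SE = √(0.889 × 0.111/9) = 0.105. Linear limits are 68%-109%, log-log limits 43%-98%, exact limits 52%-99.7%.
- Linear limits also pass 100% for 7/9 (51%-105%), 10/11 (74%-108%) and 3/4 (33%-117%).

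**Coverage.** Add the binomial probabilities of every x whose limits contain the true rate, counting zero-width or undefined intervals as misses. For n = 9 and a true rate of 0.90, the linear interval covers only at x = 6, 7, 8: 0.045 + 0.172 + 0.387 = 0.604. The log-log interval also misses at x = 6, leaving 0.560. The outcome x = 9 has probability 0.9⁹ = 0.387.

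| True rate | n | Linear % | Log-log % | Zero-width or undefined % |
|---|---|---|---|---|
| 0.90 | 9 | 60.4 | 56.0 | 38.7 |
| 0.90 | 11 | 68.3 | 66.8 | 31.4 |
| 0.85 | 4 | 47 | 37 | 52 |
| 0.85 | 6 | 62 | 58 | 38 |
| 0.92 (OS, 6 mo) | 9 | 50.9 | 48.6 | 48.7 |
| 0.92 (OS, 6 mo) | 11 | 57.7 | 53.8 | 41.5 |
| 0.85 (OS, 12 mo) | 9 | 75.7 | 73.0 | 23.8 |
| 0.85 (OS, 12 mo) | 11 | 81.3 | 76.1 | 17.3 |
| 0.81 (DOR, 6 mo) | 4 | 54.4 | 54.4 | 43.5 |
| 0.81 (DOR, 6 mo) | 6 | 70.1 | 62.9 | 28.5 |
| 0.66 (DOR, 12 mo) | 4 | 79.8 | 79.8 | 20.2 |
| 0.66 (DOR, 12 mo) | 6 | 89.9 | 89.9 | 8.3 |
| 0.36 (PFS, 6 mo) | 9 | 88.0 | 96.9 | 1.7 |
| 0.55 (PFS, 6 mo) | 11 | 87.4 | 93.5 | 0.1 |
| 0.13 (PFS, 12 mo) | 9 | 71.6 | 69.7 | 28.1 |

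Across true rates of 0.36, 0.40, 0.50 and 0.55 in the full arms, linear coverage runs from 82% to 94% and log-log from 93% to 98%. Clopper-Pearson never fell below 95% at any size or rate examined.

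**With censoring.** A Kaplan-Meier simulation with assumed uniform censoring from 3.7 to 24 months agrees. For n = 9 and a 6-month rate of 0.90, linear coverage is 60% and 40% of samples are degenerate. At a rate of 0.53, coverage is 91%. In simulations with censoring before 6 months, the beta product interval stayed above 95% for n = 4 to 11 at rates of 0.50, 0.81 and 0.90.

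**The case against.** The strongest reply has four parts.

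First, there is largely one defect, not two. At a true rate of 0.90, coverage among samples that give a usable interval is 0.604/0.613 = 99% linear and 0.560/0.613 = 91% log-log for n = 9, and higher for n = 11. This stands: low coverage is mostly the zero-event case under another name. A note saying the interval cannot be estimated would stop the false precision. It would also leave no interval exactly where 66%-100% could be reported.

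Second, the worst figures belong to high rates. This stands too. A reader might infer that these intervals under-cover in general, but the protocol's own PFS medians put 6-month PFS where log-log limits do well.

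Third, the analyses are exploratory, the primary ORR has exact limits, and swimmer plots, Kaplan-Meier plots and listings show every subject. That limits the harm but does not make a zero-width 95% interval correct.

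Fourth, an exact interval without censoring proves little if subjects are censored before 6 months. That is possible at the ad-hoc analysis, which is triggered two disease assessments after the last enrolment. The censored simulations answer this for the beta product interval, under assumed censoring patterns.

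Three other readings are tempting but not supported:
- That the reported intervals will exceed 100%. This needs linear limits, and the SAP names no scale; log-log limits cannot exceed 100%.
- That the SAP uses exact limits for ORR because the sample is small, and so contradicts itself. Protocol Section 9.6.1 already specified Clopper-Pearson when 140 and 450 subjects were planned.
- That Greenwood was carried over from the larger design. The protocol names only Kaplan-Meier methodology; Greenwood appears first in this SAP, which already records 9 and 11 subjects.

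**Conclusion.** The point holds in limited form. For DOR, PFS and OS, and by inference iDOR and iPFS, the specified interval has zero width or does not exist when no event has occurred by the time point. At a true rate of 0.90 that happens in 39% of samples of 9 and 31% of samples of 11. Coverage is then 56%-68% in the full arms; at a true rate of 0.85 it is 37%-62% with 4 to 6 responders. Very low rates suffer similarly: 12-month PFS near 0.13 gives about 70%-78%. Mid-range rates are a minor issue, especially on the log-log scale.

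The exact figures assume no censoring before the time point and count degenerate intervals as misses. The placement of plausible rates also assumes exponential curves, and 4 or 6 responders assumes the planning ORRs. The zero-variance result itself needs only that no event has occurred by the time point.

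This is a stated method that gives a wrong error bar on exploratory secondary endpoints. It should be corrected, but it does not touch the primary result.

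**What to change.** In SAP VIII.A, replace the Greenwood limits for the 6- and 12-month rates with a small-sample interval that remains valid at 0% and 100%. The beta product confidence procedure is suitable: it equals Clopper-Pearson when nobody is censored before the time point, so it matches the exact limits used for ORR, DCR and iORR. State in VIII.C that it applies to DOR, PFS, OS, iDOR and iPFS. Print the number at risk beside each rate.

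The minimum acceptable change is to name log-log limits and report an exact limit wherever the estimate is 0% or 100%. This removes zero-width intervals and limits outside 0%-100%.

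The cost is a few lines of SAP text, a short extra program and wider intervals. No endpoint, data collection or trial conduct changes.

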Immune Objective Response Rate (iORR). iORR is defined as the proportion of subjects with an immune best overall response (iBOR) of confirmed immune complete response (iCR) or confirmed immune partial response (iPR) based on immunotherapy Response Evaluation Criteria in Solid Tumors (iRECIST) by Investigator assessment.

Subjects who continue study treatment beyond PD per RECIST v1.1 will be assessed by the Investigator according to iRECIST. Subjects with an iCR or iPR per iRECIST must have a confirmatory assessment performed at least 4 weeks after the initial assessment where response was declared by the Investigator and all scans should be performed at least 2 weeks after the previous CMP-001 IT injection to prevent injection-related pseudoprogression.

The confirmed iORR will be calculated as the number of subjects with a confirmed iCR or iPR divided by the number of subjects in the analysis population [iORR = (confirmed iCR + confirmed iPR)/number of subjects] for each treatment arm of the ITT Analysis Set. The two-sided 95% Clopper-Pearson CIs will be calculated for the iORR.

The immune best overall response (iBOR) will be derived as below:

If assessments are not performed or cannot be assessed following iUPD, and there is no subsequent iCPD, iSD, iPR or iCR, iUPD will continue to be used and the subject will be censored at the date of iUPD.

Immune Duration of Response (iDOR). iDOR is defined as the time from the date of the first immune response (iCR or iPR) to the date of immune confirmed progressive disease (iCPD) based on iRECIST by Investigator assessment.

iDOR is only defined for subjects who have a confirmed iBOR of iCR or iPR. The first date on which an iCR or iPR response is noted will be used to calculate iDOR, rather than the date of the confirmatory tumor assessment. Subjects who do not develop iCPD or death will be censored at the date of their last disease assessment.

Immune Progression-Free Survival (iPFS). iPFS is defined as the time from the date of randomization to date of iCPD based on iRECIST by Investigator assessment or death from any cause, whichever occurs first.

Table 1: Censoring Rules for the PFS/DOR/iPFS/iDOR

Situation	Outcome	Date	Event Description/ Censoring Reason	PFS/ DOR	iPFS/ iDOR
PD per RECIST v1.1 on/before new anticancer therapy or data cutoff date	Event	Earliest date of tumor assessment documenting PD	PD per RECIST v1.1	X	

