Death without PD per RECIST v1.1 and not receiving new anticancer therapy on/before data cutoff date	Event	Date of death	Death without PD per RECIST v1.1	X	
iCPD per iRECIST between scheduled disease assessments on/before new anticancer therapy or data cutoff date, whichever is earlier	Event	Earliest date of tumor assessment documenting iUPD	iCPD per iRECIST		X
Death without iCPD per iRECIST and not receiving new anticancer therapy on/before data cutoff date	Event	Date of death	Death without iCPD per iRECIST		X

Regeneron Pharmaceuticals Inc. / Protocol: CMP-001-011 IQVIA Biotech (Confidential) Project # SZA58924

Subjects with no post- baseline disease assessments	Censored	First Dose Date	No Adequate Disease Assessment per RECIST v1.1	PFS Only	
No PD per RECIST v1.1 or death as of data cutoff date and subject not received new anticancer therapy or received it after the data cutoff date	Censored	Date of last disease assessment on/before data cutoff date	Alive without Documented PD	X	
No PD per RECIST v1.1 or death as of data cutoff date and new anticancer therapy started before the data cutoff date	Censored	Date of last disease assessment prior to new anticancer therapy	Subsequent Anti- cancer Therapy without Documented PD	X	
PD per RECIST v1.1 or death after new anticancer therapy and the new anticancer started before data cutoff date	Censored	Date of last disease assessment prior to new anticancer therapy	Documented PD or Death after Subsequent Anti- cancer Therapy	X	
PD per RECIST v1.1 or death after new anticancer therapy and the new anticancer started after data cutoff date	Censored	Date of last disease assessment on/before data cutoff date	Documented PD or Death after Subsequent Anti- cancer Therapy	X	
PD per RECIST v1.1 or death immediately following two or more consecutive disease assessments since the last adequate disease assessment	Censored	Date of last adequate tumor assessment prior to the first missed assessment	PD or Death after Missing >= 2 Consecutive Disease Assessments	X	
Discontinuation from study before PD per RECIST v1.1 and death	Censored	Date of last adequate disease assessment	Discontinued from Study without Documented PD or Death	X	
iUPD per iRECIST at the time of PD per RECIST v1.1, continued study treatment without further tumor assessments as of data cutoff date	Censored	Date of the last tumor assessment on/before data cutoff date	No Adequate Disease Assessment per iRECIST		iPFS Only

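### The SAP's PFS text and its Table 1 give different censoring dates for an event-free subject who misses scans and later resumes them

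*SAP*

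**What the plan says.** SAP Section VIII.A, Progression-Free Survival, handles subjects who have neither progressed nor died in two consecutive sentences. The first says they "will be censored at the date of the last adequate tumor assessment". The second says: "Date of censoring for these subjects will be based on the last tumor assessment prior to missing the assessments". The paragraph then refers to Table 1 for the censoring rules and adds a tie-break: "If a subject meets the criteria for more than one censoring rule, PFS will be censored at the earliest censoring date".

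Table 1 has a row for this subject. Its situation begins "No PD per RECIST v1.1 or death as of data cutoff date and subject not received new anticancer therapy", and its censoring date is "Date of last disease assessment on/before data cutoff date". That row makes no exception for a gap in scanning. The one PFS row that goes back to before a gap has the situation "PD per RECIST v1.1 or death immediately following two or more consecutive disease assessments since the last adequate disease assessment", so it needs a progression or a death.

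The DOR paragraph of the same section censors subjects without progression or death at their last disease assessment, as Table 1 does.

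**The concern.** Take an event-free subject who misses one or more scheduled scans and later has adequate scans showing no progression. The first text sentence and Table 1 date censoring at the last of those scans. The second text sentence, read literally, dates it at the last scan before the gap. It does not say how many missed scans make a gap, so a single one could trigger it, whereas Table 1 requires two and a subsequent event.

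A clean scan after a gap shows that the subject was progression-free through the gap. Censoring before it discards observed follow-up and takes the subject out of later risk sets, while other subjects' events in that period still count. Each arm's Kaplan-Meier curve, median and 6- and 12-month PFS rates could then depend on which sentence the programmer follows.

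Nothing else settles the choice. Protocol Section 9.6.2 leaves additional PFS censoring rules to the SAP, and SAP Section I.B says the SAP governs where the two differ. SAP Section VI.M leaves the sponsor's analysis team unblinded, so an open choice would be made with treatment assignment known.

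**Working it through.** The SAP gives no figure on this point to reproduce. The check applies each rule to one subject.

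**Inputs**
- Scan schedule (SAP Section VIII): from W10D1, then every 6 weeks, so W10, W16, W22, W28, W34, W40, W46 and W52.
- PFS formula (SAP Section VIII.A): months = (event or censoring date − randomization date + 1) / 30.4375.
- Arm sizes (SAP Section II.C): 9 in Arm A and 11 in Arm B.
- Assumptions: randomization on W1D1 and scans on their nominal days. Week w Day 1 is then day 7(w − 1) + 1.

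**Example 1: one missed scan.** Clean scans at W10 and W16, W22 missed, clean scans W28 to W52, no progression, death or new therapy.
- Second text sentence: censored at W16D1, day 7 × 15 + 1 = 106, and 106 / 30.4375 = 3.48 months.
- First text sentence and Table 1: censored at W52D1, day 7 × 51 + 1 = 358, and 358 / 30.4375 = 11.76 months.
- Difference: 11.76 − 3.48 = 8.28 months.

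**Example 2: two missed scans.** Scans at W10 and W16, W22 and W28 missed, clean scan at W34.
- Second text sentence: 3.48 months.
- Table 1: W34D1, day 7 × 33 + 1 = 232, and 232 / 30.4375 = 7.62 months.
- The two dates lie on either side of the 6-month landmark.

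**Scans stop.** Scans at W10 and W16 and none afterwards. Every rule gives W16, so there is no conflict.

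**Effect on a 6-month rate (invented arms of 9, for scale only)**
- Three progressions found at W22, and Example 1's subject among the other six. Table 1 leaves 9 at risk at W22: 1 − 3/9 = 66.7%. The second sentence leaves 8: 1 − 3/8 = 62.5%. The shift is 4.2 points.
- Progressions at W10 (two), W16 and W22, four subjects censored at W52, and Example 2's subject. Table 1: 7/9 × 6/7 × 5/6 = 55.6%. Second sentence: 7/9 × 6/7 × 4/5 = 53.3%.

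Within an arm the direction is fixed. The events stay the same and the risk sets can only shrink, so the second sentence can lower the Kaplan-Meier estimate or leave it unchanged, never raise it. The 12-month rate moves in the same way if others progress between W28 and W52.

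**Comparison with DOR.** Suppose Example 1's subject responded at W10 and was confirmed at W16. DOR runs from day 64 to day 358: (358 − 64 + 1) / 30.4375 = 9.69 months. PFS under the second sentence is 3.48 months, shorter than the response it contains. The PFS sentence is therefore the outlier.

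**The case against.** The best defence is that the second sentence merely explains the first for subjects whose scans stop. Read that way, text and table agree. That reading is reasonable and probably intended, but the sentence is not limited to it and says something different for a subject who resumes scanning.

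It is also fair that the effect is small. The 4.2-point shift comes from an invented arm and compares with a Greenwood standard error of about 16 points at 6/9 (0.667 × √(3 / (9 × 6)) = 0.157). PFS is a secondary, descriptive summary in 20 subjects, and the SAP calls every analysis exploratory.

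A reader might infer four stronger points that the documents do not support:

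- *The tie-break forces the earlier date.* It follows directly on the reference to Table 1. In Table 1, a subject still on study without new therapy who resumes clean scans fits only the last-assessment row. Whether the text sentence counts as a separate censoring rule is not stated.
- *Progression after new therapy is left open between event and censoring.* The event row, "PD per RECIST v1.1 on/before new anticancer therapy or data cutoff date", lacks the 'whichever is earlier' found in the iCPD row and literally overlaps "PD per RECIST v1.1 or death after new anticancer therapy and the new anticancer started before data cutoff date". But the PFS paragraph excludes assessments made after new therapy, and the second of these rows specifically censors the case. For PFS there is one answer. The DOR paragraph has no such exclusion, but the specific censoring row is marked for DOR too.
- *Progression after two completed scans is censored.* The situation cell omits the word 'missed', but the same row's date cell refers to the first missed assessment and its reason cell to missing at least two. The intent is plain.
- *DOR has the same conflict.* The pre-gap sentence and the tie-break stand only in the PFS paragraph, and the DOR text agrees with Table 1.

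**Conclusion.** The inconsistency is real but narrow. For event-free subjects who miss scans and later resume, the second text sentence contradicts the sentence before it, and Table 1 where no new therapy was started. Applied literally, it gives a PFS time that is too short: 3.48 instead of 11.76 months in the one-missed-scan example, given randomization on W1D1 and nominal scan days. How many subjects are affected cannot be known from the documents. One subject is 1/9 = 11.1% of Arm A or 1/11 = 9.1% of Arm B, so a single case can move a reported rate or median. No confirmatory claim depends on it, and the impact is minor. It still merits correction, because a stated rule would give a wrong time and the repair needs only wording.

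**What to change.** In SAP Section VIII.A, Progression-Free Survival, delete the second sentence. Alternatively, restrict it to progression or death after two or more missed assessments, so that it matches Table 1. In either case, state that a later adequate progression-free scan closes the gap.

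Two tidy-ups in Table 1 leave the intended result unchanged: add 'whichever is earlier' to the PD event row, and insert 'missed' in the two-assessment row and its iPFS/iDOR counterpart.

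The cost is a few wording edits to the SAP, with no new data. They should be made before the PFS output is programmed.
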